NON-INTERVENTIONAL (NI) STUDY PROTOCOL

Study Information

Title	Administration of Elranatamab In the Real-World: Treatment Patterns, Healthcare Resource Utilization, Costs, Effectiveness, and Safety (ALTITUDE).
Protocol number	C1071039
Protocol version identifier	V2.0
Date	31 July 2025
EU Post Authorization Study (PAS) register number	EUPAS1000000229
Active substance	L01FX32
Medicinal product	ELREXFIO™ (elranatamab)
Research question and objectives	
Research Question: What are the patient characteristics, treatment characteristics, safety, effectiveness, healthcare resource utilization (HCRU), and costs of patients with relapsed/refractory multiple myeloma (RRMM) who initiate elranatamab using Komodo Health administrative claims data?
 
The following objectives will be assessed among patients with RRMM receiving elranatamab:
 
Primary
 
• Objective 1: Describe the demographics, clinical history, and treatment history of patients in the study• Objective 2: Describe the administration and treatment management of elranatamab• Objective 3: Describe all-cause and MM-related HCRU and costs by

	
place of service of patients in the study
 
Exploratory
 
• Exploratory Objective 1: Describe the tolerability and real-world safety of elranatamab• Exploratory Objective 2: Describe the effectiveness of elranatamab in terms of time to next treatment or death (TTNT/D) and overall survival (OS)• Exploratory Objective 3: In a separate cohort, replicate all objectives for patients with the same indication as elranatamab who initiated teclistamab
Country(ies) of study	United States (US)
Author	Redacted [REDACTED] [REDACTED] [REDACTED]

2. LIST OF ABBREVIATIONS

Abbreviation	Definition
AE	Adverse Event
ALT	Alanine Aminotransferase
ALTITUDE	Administration of Elranatamab In the Real-World: Treatment Patterns, Healthcare Resource Utilization, Costs, Effectiveness, and Safety
AST	Aspartate aminotransferase
BCMA	B-Cell Maturation Antigen
BsAb	Bispecific Antibody
CAR-T	Chimeric Antigen Receptor T-Cell Therapy
CCI	Charlson Comorbidity Index
CI	Confidence Interval
CPT	Current Procedural Terminology
CRS	Cytokine Release Syndrome
EC	Ethics Committee EMA
ED	Emergency Department
EMA	European Medicines Agency
FDA	Food and Drug Administration
GPP	Good Pharmacoepidemiology Practices
HCPCS	Healthcare Common Procedure Coding System
HCRU	Healthcare Resource Utilization
HMA	The Heads of Medicines Agencies
ICANS	Immune Effector Cell-Associated Neurotoxicity Syndrome

PFIZER CONFIDENTIAL

Redacted

Abbreviation	Definition
ICD-10	International Classification of Diseases, 10th Edition
IgA	Immunoglobulin A
IgG	Immunoglobulin G
IgE	Immunoglobulin E
IgM	Immunoglobulin M
IMiDs	Immunomodulatory Agent
IP	Inpatient
IQR	Interquartile Range
IRB	Institutional Review Board
IV	Intravenous
mABs	Monoclonal Antibody
MG	Milligram
ML	Milliliter
MM	Multiple Myeloma
M protein	Monoclonal Protein
NDC	National Drug Code
NCCN	National Comprehensive Cancer Network
OP	Outpatient
ORR	Objective Response Rate
OS	Overall Survival
PASS	Post-Authorisation Safety Study

Abbreviation	Definition
PIs	Proteasome Inhibitors
PJP	Pneumocystis Jiroveci Pneumonia
PPPM	Per-Patient-Per-Month
RAI	Relative Administration Intensity
RRMM	Relapsed And Refractory Multiple Myeloma
RWD	Real World Data
SEER	Surveillance, Epidemiology, and End Results
TTD	Time to Discontinuation
TTNT/D	Time To Next Treatment/Death
SD	Standard Deviation
US	United States

4. ABSTRACT

Title: Administration of Elranatamab In the Real-World: Treatment Patterns, Healthcare Resource Utilization, Costs, Effectiveness, and Safety (ALTITUDE)

Version: v2.0

Date: 31 July 2025

Author: Redacted

Rationale and background: Elranatamab is a B-Cell Maturation Antigen (BCMA) bispecific antibody (BsAb) that was approved in the US for patients with MM who have been treated with at least four lines of therapy, including a proteasome inhibitor (PIs), an immunomodulatory agent (IMiD), and an anti-CD38 monoclonal antibody (mAb). A limited number of studies have been published assessing the real-world utilization of elranatamab due to its recent approval. This study will describe the real-world usage, patient outcomes, and HCRU associated with elranatamab in the US by leveraging an up-to-date healthcare claims dataset.

Research question and objectives: What are the descriptive characteristics, treatment patterns, all cause/MM-related, HCRU, safety and effectiveness of elranatamab therapy?

The study objectives are to:

Primary

- **Objective 1:** Describe the demographics, clinical history, and treatment history of patients in the study
- **Objective 2:** Describe the administration and treatment management of elranatamab
- **Objective 3:** Describe all-cause and MM-related HCRU and costs by place of service of patients in the study

Exploratory

- **Exploratory Objective 1:** Describe the tolerability and real-world safety of elranatamab
- **Exploratory Objective 2:** Describe the effectiveness of elranatamab in terms of TTNT/D and OS
- **Exploratory Objective 3:** In a separate cohort, replicate all objectives for patients with the same indication as elranatamab who initiated teclistamab

Study Design: This will be a retrospective descriptive cohort study using de-identified US claims data from Komodo Health.

Population: This study will include adult (≥ 18 years old) patients with an International Classification of Diseases, tenth revision (ICD-10) code for RRMM (defined as MM ICD-10 codes: C90.0x). The study cohort will include patients with RRMM who initiate elranatamab between 14 August 2023 (US approval date) and end of data (defined as the latest data available, at the time of the specified analysis). Exploratory analyses will also include a teclistamab-exposed cohort, which will include patients with RRMM who initiate teclistamab between 14 August 2023, and the end of data. The index date for patients in each cohort will be defined as the date of the first prescription or medical claim for elranatamab or teclistamab. Patients will be required to have at least 180 days of continuous closed-claims enrollment before the index date.

Variables: Variables used to define eligibility will include elranatamab, MM diagnosis, and observability.

Variables to define demographic and clinical characteristics will include, but are not limited to, age, sex, race/ethnicity, region, Charlson Comorbidity Index (CCI), and prior infections.

Prior treatment history will be captured based on the use of National Comprehensive Cancer Network (NCCN) guideline-recommended treatments, which include chimeric antigen receptor T cell therapy (CAR-T), PIs, and IMiDs.

HCRU and costs will be described overall and by place of service, including inpatient (IP) visits, outpatient visits (OP, defined as non-IP/non-ED), emergency department (ED) visits, and pharmacy claims. Additionally, HCRU and imputed costs will be reported as all-cause and MM-related.

Adverse events (AEs) will include cytokine release syndrome (CRS), immune effector cell-associated neurotoxicity syndrome (ICANS), peripheral neuropathy, and infections. Effectiveness outcomes will include TTNT/D and OS.

Country of Study: US

Data Sources: This study will use Komodo Health data. The data source is a healthcare technology firm that owns, links, and integrates open and closed-claims databases from over 150 public and private payers/insurers and clearinghouses across the US. The database is closely aligned with the population of the National Health Interview Survey in terms of geography and demographics. This source of insurance claims data encompasses comprehensive, longitudinal records detailing medical procedures, diagnoses, treatments, and associated costs within the healthcare system, as well as patient characteristics and outcomes such as race/ethnicity, zip code, and all-cause mortality records.

The current cut of the data includes over 700,000 patients with MM. The results of this study may be updated as additional data become available for elranatamab.

Study Size: This is a retrospective descriptive cohort study; therefore, sample size calculations are not applicable. As of 24 April 2024, the dataset included 56 patients with a claim for elranatamab.

Data Analysis: Categorical and binary variables will be summarized by the number and percentage of patients in each category. Continuous variables will be described using mean, standard deviation (SD), median, interquartile range (IQR), minimum, and maximum. If applicable, the frequency and percentage of patients with missing data for each variable will be described. Relative Administration Intensity (RAI) will be calculated as the ratio of the actual number of administrations during each time period divided by the expected number of administrations based on the label for the treatment. All-cause HCRU and MM-related HCRU will be measured as the mean, SD, median, IQR, minimum, and maximum of the total number of IP, OP, ED, and pharmacy claims that occurred over the follow-up period and in the 180-day baseline period. Given the variable follow-up time available for each patient, HCRU and costs will be reported per-patient-per-month (PPPM). The prevalence and incidence, as well as the associated 95% confidence intervals (CI) for each AE, will be estimated. Kaplan-Meier methods will be used to estimate the median time to event, including 95% CIs for TTNT/D, TTD, and OS. All analyses will be repeated in an exploratory cohort of patients receiving teclistamab.

Milestones: Data analysis will begin after protocol finalization by 15 August 2024. There will be one initial set of results and four subsequent quarterly refreshes with updated data throughout 2025. At the end of implementation, a final report will be generated by 28 February 2026.

5. AMENDMENTS AND UPDATES

Version Identifier	Date	Amendment Type (substantial or administrative)	Protocol Section(s) Changed	Summary of Amendment(s)	Reason
2.0	31 July 2025	Administrative	2	Addition of abbreviations in the list of abbreviations	Updated to reflect new variables and some not previously defined.
2.0	31 July 2025	Administrative	3	Update of the study team roster	Updated to reflect departures or additions to the team.
2.0	31 July 2025	Substantial	4	Version and date were updated. Small wording updates were made to clarify the definition of “end of data” and to further describe the four prespecified study quarterly refreshes.	The set end date was removed and replaced with flexible language reflecting the amendment to conduct quarterly updates.
2.0	31 July 2025	Substantial	6	Update of the milestone dates and inclusion of the four study refreshes	Four quarterly refreshes have been added.
2.0	31 July 2025	Substantial	8	Minor updates to the objectives wording	This section was updated to improve clarity
2.0	31 July 2025	Substantial	9.2 (inclusive of subsections)	clarified the definition of the end of the study	The set end date was removed and

PFIZER CONFIDENTIAL

Redacted

				period; formatting changes to reflect Pfizer's protocol template.	replaced with flexible language reflecting the amendment to conduct quarterly updates.
2.0	31 July 2025	Substantial	9.3: Table 2	Added baseline lab assessments, certain clinical characteristics defined by the results of specific laboratory tests and insurance type in Table 2. Minor update to assessment periods. Addition of a footnote to flag variables that are assessed during follow-up.	Data was received from the vendor containing information on laboratory test results and patterns. Minor changes were made to assessment periods and to further clarify assessment periods of baseline characteristics.
2.0	31 July 2025	Substantial	9.3: Table 3	Study variables added: the proportion of patients with two administrations, IP visit information from different Komodo tables, and HCRU during the step-up dosing period.	Better captures measures of interest based on data explorations.
2.0	31 July 2025	Substantial	9.5	Study end date replaced with flexible language	The set end date was removed and replaced with flexible

					language reflecting the amendment to conduct quarterly updates.
2.0	31 July 2025	Substantial	9.7.1	Additional lab variable subgroup in the baseline characteristics	This subgroup will help contextualize any difference with respect to lab availability
2.0	31 July 2025	Substantial	9.7.2: Figure 2	The study figure was updated The time period of assessment for duration on treatment and censoring reasons as clarified.	To clarify the exact end dates for each dosing period, reflecting ELREXFIO label. The set end date was removed and replaced with flexible language reflecting the amendment to conduct quarterly updates.
2.0	31 July 2025	Substantial	9.7.3	RAI assessment added. Censoring criteria for RAI was updated to include the last administration of the index treatment. Study end date replaced with flexible language	The addition of this analysis better help contextualize the “upper” bound of RAI. Last administration of the index treatment was included as a censoring criterion as many patients

					have long periods of no treatment from their last administration to the censor date. RAI estimates seemed to be underestimated due to this factor.
2.0	31 July 2025	Substantial	9.7.4	Removal of the phrase stating "If follow-up time is adequate" Study end date replaced with flexible language	Patients will be included in the TTD assessment regardless of duration of follow-up. The set end date was removed and replaced with flexible language reflecting the amendment to conduct quarterly updates.
2.0	31 July 2025	Substantial	9.7.5	A sentence to clarify pharmacy claim capture for HCRU was included. A sentence rationalizing the usages of PPPM estimates was included. An additional time period for HCRU	The additional sentences were for clarification. The new time of assessment was a request based on interest in measuring HCRU during the step-up period.

				assessment was included. Study end date replaced with flexible language	The set end date was removed and replaced with flexible language reflecting the amendment to conduct quarterly updates.
2.0	31 July 2025	Substantial	9.7.5	Study end date replaced with flexible language	The set end date was removed and replaced with flexible language reflecting the amendment to conduct quarterly updates.
2.0	31 July 2025	Substantial	9.7.6	Study end date replaced with flexible language	The set end date was removed and replaced with flexible language reflecting the amendment to conduct quarterly updates.
2.0	31 July 2025	Administrative	ANNEX	Inclusion of the most update to date ANNEX containing study variables. Multiple Myeloma codes were added into the Any Malignancy component for the CCI score.	Data was received from the vendor containing information on laboratory test results and patterns. MM codes were added into the CCI

					definition to accurately reflect the published definition of CCI.
--	--	--	--	--	---

6. MILESTONES

Milestone	Planned Date
Start of data collection	15 August 2024
Registration in The Heads of Medicines Agencies (HMA)-European Medical Agency (EMA) Catalogues of Real World Date (RWD) studies	26 July 2024
Interim results delivery	23 September 2024
Full results delivery	15 November 2024
Full result refresh 1	15 January 2025
Full result refresh 2	09 April 2025
Full result refresh 3	09 September 2025
End of data collection	20 November 2025
Full result refresh 4	20 December 2025
Final study report	28 February 2026

7. RATIONALE AND BACKGROUND

MM is a hematological malignancy originating in plasma cells in the bone marrow.^{1,2} Healthy plasma cells secrete antibodies, also known as immunoglobulins, to fight infection and act as the humoral line of defense.^{1,2} Plasma cells that have become cancerous (ie, myeloma cells) proliferate and displace normal cell production in bone marrow, among other effects on the immune system. As a consequence, the general production of antibodies is impaired, decreasing the body's supply of antibodies.³ MM is characterized by an increase in non-functional monoclonal proteins (M proteins), a decrease in blood count, renal failure, end-organ damage, susceptibility to infections, and bone weakness.¹⁻³ The incidence of MM was 7.4 per 100,000 people in the US from 2016-2020, while the 5-year relative survival from 2013 to 2019 was 59%.⁴ MM is the second most prevalent hematological malignancy and accounted for approximately 1.8% of all new cancer cases in 2023.^{5,6}

Many therapies for MM exist, and clinical advances continue to change the treatment landscape. The advent of therapies, such as proteasome inhibitors (PIs), IMiDs, and mAbs, has increased the OS of MM patients.⁷⁻⁹ Despite numerous advances in the available therapies for MM, most patients with MM will either relapse (fail to respond to treatment) or become refractory (have their treatment fail).¹⁰ These patients are collectively referred to as having RRMM. Given relapse to later lines confers progressively worse outcomes including shorter survival time, there is a need to investigate alternative treatment options in this setting.^{9,10}

Recent improvements in treatment for patients with RRMM included advances in B-based treatments targeting BCMA, which is primarily present in malignant plasma cells. BCMA is expressed in B-cells and regulates their maturation into plasma cells.¹¹ BCMA BsAbs target and bind BCMA-expressing plasma cells and the CD3 receptor on T-cells, activating cytotoxic activities of the T cell.¹¹ Elranatamab is a BCMA BsAb indicated for patients who have received at least four lines of therapy, including a PI, an IMiD, and an anti-CD38 mAbs.¹² Elranatamab was approved in August of 2023, based on the results from the MagnetisMM-3 trial, a phase 2 trial aimed at assessing the efficacy of elranatamab monotherapy. The Objective Response Rate (ORR) was 61.0%, and common AEs included infections (69.9%) CRS (57.7%), anemia (48.8%), and neutropenia (48.8%).¹³ While some published studies have assessed the real-world utilization of other BCMA BsABs such as teclistamab, the real-world usage of elranatamab has not been characterized.^{14,15} This study aims to describe the uptake and use of elranatamab subsequent to the August 2023 Food and Drug Administration (FDA) approval using recent data reflecting real-world clinical practice.

This noninterventional study is designated as a PASS and is conducted voluntarily by Pfizer.

8. RESEARCH QUESTION AND OBJECTIVES

Research Question: What are the descriptive characteristics, treatment patterns, all cause/MM-related HCRU, safety and effectiveness of elranatamab therapy?

The study objectives are to:

Primary

- **Objective 1:** Describe the demographics, clinical history, and treatment history of patients in the study
- **Objective 2:** Describe the administration and treatment management of elranatamab
- **Objective 3:** Describe all-cause and MM-related HCRU and costs by place of service of patients in the study

Exploratory

- **Exploratory Objective 1:** Describe the tolerability and real-world safety of elranatamab
- **Exploratory Objective 2:** Describe the effectiveness of elranatamab in terms of TTNT/D and OS
- **Exploratory Objective 3:** In a separate cohort, replicate all objectives for patients with the same indication as elranatamab who initiated teclistamab

9. RESEARCH METHODS

9.1. Study Design

This retrospective descriptive cohort study will assess the demographic, clinical, treatment characteristics, HCRU, costs, effectiveness, and safety of MM patients with an elranatamab claim and will use de-identified data from Komodo Health.

9.2. Setting

This study will evaluate adult patients with RRMM who initiate elranatamab. Patients will enter (i.e., index) on the first observed elranatamab claim between 14 August 2023 and the end of data (defined as the latest data at the time of the specified analysis). Limited eligibility criteria will be applied.

Study Period: Start of data availability (01 January 2016) to the end of data

MM diagnosis window: Start of data availability (01 January 2016) to index date

Index date: First elranatamab claim after initial MM diagnosis

Observability: At least 180 days of continuous closed-claims medical and pharmacy enrollment prior to index (inclusive)

[figure not shown]
Baseline period for MM-related treatments and MM-related comorbidities: MM diagnosis to one day prior to index date (unless otherwise specified)

CCI and baseline HCRU assessment window: 180 days prior to index date to index date.

Follow-up: Index date until death, the earliest of the end of data, or end of continuous enrollment (unless otherwise noted). Alternative censoring criteria will be applied for certain outcomes (such as OS, TTD, and TTNT/D); see [Section 9.7](#) for more details.

Figure 1 reflects the time periods of interest in the study cohort.

Figure 1. Study Schematic for Patients Receiving Elranatamab

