3	TTD	Time in months from first administration until last administration prior to treatment discontinuation (continuous). Treatment discontinuation is defined as an 8-week gap in elranatamab (or for the exploratory analysis, teclistamab therapy), next treatment after index treatment (CAR-T, BsABs, bendamustine or belantamab), or death.	Index date to the end of follow-up. Follow-up will be defined based on the censoring criteria described in Section 9.7.4
Health care resource utilization and costs			
4	All-cause IP visits	Medical claim for IP (non-ED) visit (dichotomous)	180 days prior to index date to 1 day prior to index date
		Number of IP (non-ED) visits (continuous)	Step-Up Dosing Period Index date to end of follow-up. Follow-up will be defined two ways to account for gaps in elranatamab use. See Section 9.7.5 for censoring criteria
4	IP visits from the IP table	Medical claim for IP (non-ED) visit sourced from the IP table (dichotomous)	180 days prior to index date to 1 day prior to index date
		Number of IP (non-ED) visits sourced from the IP table (continuous)	Step-Up Dosing Period Index date to end of follow-up. Follow-up will be defined two ways to account for gaps in elranatamab use. See Section 9.7.5 for censoring criteria
4	IP visits from the Non-IP table	Medical claim for IP (non-ED) visit sourced from the Non-IP table where place of service indicates an IP setting (dichotomous)	180 days prior to index date to 1 day prior to index date

		Number of IP (non-ED) visits sourced from the IP table place of service indicates an IP setting (continuous)	Step-Up Dosing Period Index date to end of follow-up. Follow-up will be defined two ways to account for gaps in elranatamab use. See Section 9.7.5 for censoring criteria
4	All-cause OP visits	Medical claim for non-IP/non-ED visit (dichotomous)	180 days prior to index date to 1 day prior to index date
		Number of non-IP/non-ED visits (continuous)	Step-Up Dosing Period Index date to end of follow-up. Follow-up will be defined two ways to account for gaps in elranatamab use. See Section 9.7.5 for censoring criteria
4	All-cause ED visits	Medical claim for ED visit (dichotomous)	180 days prior to index date to 1 day prior to index date
		Number of ED visits (continuous)	Step-Up Dosing Period Index date to end of follow-up. Follow-up will be defined two ways to account for gaps in elranatamab use. See Section 9.7.5 for censoring criteria
4	All-cause pharmacy claims	Pharmacy claim (dichotomous)	

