9.7.2. Treatment Exposure Outcomes

Treatment exposure outcomes include RAI and time between administrations. The assessment periods shown in Table 4 are based on the elranatamab label instructions and will be used to measure treatment and dosing-related outcomes for patients receiving elranatamab.¹⁸ These periods are also provided in Figure 2.

[figure not shown]
Table 4. Dosing Schedule and Expected Administrations and Vial Size of Elranatamab

Dosing Schedule	Time Period	Expected Administrations	Vial Size

[figure not shown]
Step-Up	Index date - Day 8	3 during Step-Up	44mg/1.1mL
Maintenance Period 1	Day 9 - Day 168	1 per week	76mg/1.9mL
Maintenance Period 2	Day 169 – Censor	1 every two weeks	76mg/1.9mL

Figure 2. Dosing Schedule for Elranatamab and Teclistamab

Elranatamab label instructions

Teclistamab label instructions

The assessment periods shown in Table 5 are based on the teclistamab label instructions and will be used to measure treatment and dosing-related outcomes for patients receiving teclistamab.¹⁹ These periods are also provided in Figure 2.

Table 5. Dosing Schedule and Expected Administrations and Vial Size of Teclistamab

Dosing Schedule	Time Period	Expected Administrations	Vial Size
Step-Up	Index date - Day 7	3	30 mg/3mL
Maintenance Period	Day 8 - Censor	1 per week	153 mg/1.7mL

Dosing outcomes (reported vial size, average time between claims, and frequency of claims) will be assessed during the above time periods regardless of whether the number of administrations during the period matches the number indicated on the label instructions. Duration on treatment will be measured from the first administration to the last administration of the index drug.

Patients will be censored at the earliest of death, next treatment (CAR-T, BsABs, bendamustine, or belantamab), the end of observability, or the latest data at the time of the specified analysis.

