9.7.5. Healthcare Resource Utilization and Cost

All-cause HCRU and MM-related HCRU (ie, HCRU with a diagnosis code or treatment for MM) will be measured as the total number of IP, OP, ED, and pharmacy claims that occurred over the follow-up period. Medical claims will only be counted once per day to estimate

visits, pharmacy claims will count all claims including multiple on the same day. Additionally, the total length of IP stays will be reported among patients with at least one IP visit. Given the recency of the study period, costs will not be adjusted for inflation. As the number of HCRU claims will vary by patient follow up time, results will also be reported as PPPM.

HCRU and associated costs will be measured across four different time periods. The first time period will be from 180 days prior to index date to one day prior to the index date, the second time period will be the index date until last recorded dose, the third time period will be during the step-up dosing period, the fourth time period will be the index date until discontinuation with an allowable 8-week gap of the index drug.

Patients will be censored at the earliest of death, next treatment (CAR-T, BsABs, bendamustine or belantamab), the end of continuous closed-claim coverage, or the latest data at the time of the specified analysis.

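### Section 9.2 ends the baseline resource-use window on the index date, while Table 3 and Section 9.7.5 end it the day before; following 9.2 would count the first-dose day in both baseline and follow-up.

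*Protocol*

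**What the plan says.** Section 9.2 gives a single line for two different measures: "CCI and baseline HCRU assessment window: 180 days prior to index date to index date". That line carries no clause letting another section override it.

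Section 9.7.5, which defines the HCRU and cost analysis, says: "The first time period will be from 180 days prior to index date to one day prior to the index date". In Section 9.3, the HCRU and cost rows of Table 3 give the baseline window as "180 days prior to index date to 1 day prior to index date". The abstract describes the baseline period as 180 days long.

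The on-treatment periods all open on the index date:
- Section 9.7.5: "the second time period will be the index date until last recorded dose". The fourth period there, up to discontinuation, has the same start.
- Table 4 in Section 9.7.2, which fixes the elranatamab step-up period used as the third HCRU period: "Index date - Day 8". Table 5 starts the teclistamab step-up on the index date as well.
- Section 9.2, general follow-up: "Follow-up: Index date until death, the earliest of the end of data, or end of continuous enrollment (unless otherwise noted").

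The index date itself is defined in Section 9.2: "Index date: First elranatamab claim after initial MM diagnosis".

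**The concern.** The index date is not an ordinary day. By definition it is the day the study drug is first billed, and Table 2 records the care setting of that administration, which may be inpatient. If the baseline window includes that day, the cost of the first dose and its administration enters a figure meant to describe patients before treatment. The same claims then appear again in the on-treatment periods. A patient whose first dose was given in hospital, with no admission in the preceding 180 days, would be recorded as having a baseline inpatient visit.

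HCRU and costs by place of service are primary Objective 3, and this window is its only pre-treatment period. Exploratory Objective 3 repeats all objectives for teclistamab, so the same ambiguity carries over to that cohort.

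**Working it through.** **1. Day count, with the index date as day 0.**

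| Source | Window | Days | Shared with follow-up (from day 0) |
|---|---|---|---|
| Table 3 and Section 9.7.5 | −180 to −1 | 180 | none |
| Section 9.2 as worded | −180 to 0 | 181 | day 0 |

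The first row reproduces the abstract's 180-day baseline; the second does not. If the 30.4375-day month that Section 9.7.4 states for time to discontinuation is also assumed for per-patient-per-month (PPPM) figures, the lengths are 180/30.4375 = 5.914 months and 181/30.4375 = 5.947 months.

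**2. Does 9.2 mean to include the index date?** The line just above it in Section 9.2, for MM-related treatments and comorbidities, shows how that section excludes the day: "MM diagnosis to one day prior to index date (unless otherwise specified"). Table 2 gives CCI the same end point as the 9.2 line. The CCI half of the line is therefore consistent with the rest of the protocol, and the HCRU half is the outlier.

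**3. Effect on baseline cost if 9.2 were followed.** Let B be a patient's total cost over days −180 to −1, D the cost on the index date, and k = D/(B/180), the index-day cost as a multiple of the mean baseline day. Neither B nor D is in the documents, so k is an assumption.

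- Relative rise in the baseline total: (B + D)/B − 1 = k/180.
- Relative rise in baseline PPPM: [(B + D)/181]/[B/180] − 1 = (180 + k)/181 − 1. The month length cancels.

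| k (assumed) | Rise in total | Rise in PPPM |
|---|---|---|
| 1 | 1/180 = 0.6% | 181/181 − 1 = 0% |
| 10 | 10/180 = 5.6% | 190/181 − 1 = 5.0% |
| 30 | 30/180 = 16.7% | 210/181 − 1 = 16.0% |
| 60 | 60/180 = 33.3% | 240/181 − 1 = 32.6% |

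The PPPM rise is slightly smaller than the rise in the total because the extra day also lengthens the denominator. It disappears when the index day costs no more than an average baseline day.

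**The case against.** The sections that define the analysis already state a workable window. Section 9.7.5 and the Table 3 rows agree with each other and with the abstract, so an analyst would have to set them aside in favour of a summary line to produce the double count. This stands, and it limits the practical risk.

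It can also be said that 9.2 does not clearly include the index date. The observability line in the same section adds that its window is inclusive, and this line does not. The MM diagnosis window in 9.2 also runs to the index date, while inclusion criterion 3 asks for a diagnosis before it, so the phrase may be used loosely. This carries less weight, because the neighbouring line in 9.2 names the day before index when that is what it means.

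A reader might go further and infer that a before/after contrast is biased, or that reported baseline costs are wrong by a known dollar amount. The documents support neither. Objective 3 is descriptive, Section 9.7 plans no formal comparisons between groups, and no baseline-to-follow-up difference is specified. The protocol gives no cost figures and no share of patients starting in hospital. Nor does it show that any delivered result used the 9.2 window.

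**Conclusion.** The contradiction is real and lies in the current text. Section 9.2 gives a 181-day baseline HCRU window that overlaps every on-treatment period on the index date. Table 3, Section 9.7.5 and the abstract fit a 180-day window with no overlap. Section 9.8 says the protocol will be strictly followed, which is not possible while it states two windows.

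The consequence is conditional. Only if 9.2 were applied would the descriptive baseline use and cost for a primary objective absorb the first-dose day. The size cannot be derived from the documents; the percentages above rest entirely on the assumed k. This is an inconsistency to correct, not a flaw in the design, because the window in Table 3 and 9.7.5 is sound.

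**What to change.** Split the line in Section 9.2 into two:
- CCI: day −180 through the index date, as in Table 2.
- Baseline HCRU and costs: day −180 through the day before the index date (180 days), as in Table 3 and Section 9.7.5.

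Check that Figure 1, which is not visible in the text reviewed, shows the same windows. State that baseline PPPM is the baseline total divided by the length of the 180-day window in months, and give the month length used, since 30.4375 days is stated only for time to discontinuation. Confirm which window the results already delivered used.

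The cost is a short protocol correction with no new data. Version 2.0 is dated 31 July 2025, and refreshes 3 and 4 (9 September and 20 December 2025) and the final report (28 February 2026) are scheduled after it. If the code already follows Table 3 and 9.7.5, nothing needs to be rerun.
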